12.2.2 IcICLE Extension Study

The primary endpoint is the dichotomous variable, MRD Negativity. The precise specification for determining whether a patient is MRD-negative is detailed in section 7.2.3.

We will judge the rate of activity of the experimental regimen using this outcome measure. Under Ibrutinib alone, we would expect a negligible proportion of patients to become MRD-negative. We will regard the combined regimen as worthy of further clinical investigation in a larger, randomised trial if we find reasonable evidence that the rate of activity exceeds 20%.

We will analyse the activity rate of MRD Negativity using a Bayesian method. With binomial data, we can express our prior beliefs on activity using a Beta distribution and use the conjugacy property to express our posterior beliefs as another Beta distribution.

The experimental regimen has not been investigated before so we have no strong prior information. As such, we will use a weakly-informative prior. This is achieved using a Beta(1, 1) distribution, equivalent to saying a-priori that we consider no activity rate to be any more or less likely than any other. After n patients have completed treatment, r of whom become MRD-negative, our posterior beliefs about the activity rate will be described by a Beta(1+r, 1+n-r) distribution. At the end of the trial, we will declare the regimen as showing sufficient activity to warrant further investigation if we are at least 50% confident that the level of activity exceeds 20%. We refer to this as the activity decision rule.

It is possible but not expected that fewer than 40 patients will actually register to this study. For instance, there might be unanticipated and unavoidable shortfalls in recruitment. A benefit of using the Bayesian method is that we will be able to handle deviations from target recruitment in a consistent manner by invoking the Bayesian decision rule described above on the available data.

For all trial sizes between 30 and 40 patients inclusive, the activity decision rule has the following operating characteristics:

- If the true activity rate is 30%, the probability of approving the regimen is always greater than 90%;
- If the true activity rate is 10%, the probability of approving the regimen is always less than 10%;
- The rule never approves the regimen when observing responses in fewer than 18.7% of patients.

It is our intention to invoke the activity decision rule when the target level of recruitment has been achieved and sufficient follow-up has been completed to inform activity status for all patients. If the target level of recruitment is not possible, the decision rule should be invoked on the fullest possible data-set, i.e. after the maximum number of patients have been recruited and followed-up for as long as possible to inform activity status to the greatest extent.

Some illustrations of the activity decision rule are given in Table 8. The variable θ is the activity rate of MRD-negativity.

Table 8: Illustrations of the activity decision rule under different assumed trial outcomes with prior beliefs $\theta \sim \text{Beta}(1,1)$

Total Patients, n	Patients achieving MRD-negativity, r	Posterior Beliefs for $\theta r, n$	Prob($\theta r, n > 0.2$)	Decision
40	8	Beta(9, 33)	56.19%	Approve treatment
40	7	Beta(8, 34)	40.69%	Reject treatment
37	7	Beta(8, 31)	50.03%	Approve treatment
35	6	Beta(7, 30)	40.07%	Reject treatment

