The largest and most meaningful dataset to assess the safety of obinutuzumab in combination (with chlorambucil) therapy in patients with CLL comes from study BO21004/CLL11.

Fatal AEs occurred in 5.7% and 7.5% of patients in the GC1b and RC1b arms, respectively. The incidence of SAEs in the GC1b and RC1b arms was 42.0% and 36.8% respectively, the incidence of Grade 3-4 AEs was 70.5% and 56.7% respectively, and the incidence of AEs leading to withdrawal of any study medication was 20.2% and 15.3%, respectively.

Imbalances between the treatment arms in AEs, SAEs and Grade 3-5 AEs was mainly due to IRRs, which occurred primarily during the first infusion of obinutuzumab. IRRs were experienced by 238/336 patients (70.8%) who received GC1b and led to the treatment withdrawal of 27/336 patients (11.3%).

Infusion Related Reactions

In both monotherapy and combination therapy studies the most frequently observed adverse events in patients receiving obinutuzumab were infusion-related reactions (IRR). ; These occurred predominantly during infusion of the first 1000 mg. The incidence and severity of infusion related symptoms decreased substantially with subsequent infusions, with most patients having no IRRs during the second and subsequent administrations of obinutuzumab. Patients with a high tumour burden (i.e. high peripheral lymphocyte count in CLL ($> 25 \times 10^9/L$) may be at increased risk of severe IRR. The commonly experienced IRRs are characterised by hypotension, fever, chills, flushing, nausea, vomiting, hypertension, and fatigue, among other symptoms. In the majority of patients, IRRs were mild or moderate and could be managed. Hypersensitivity may be difficult to distinguish from infusion related reactions; anaphylaxis has been reported in patients treated with obinutuzumab.

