7.2.3.2 MRD analysis reports from HMDS

The following diagnostic categories will be used on HMDS reports to define MRD status:

- B-cell chronic lymphocytic leukaemia (B-cell CLL)
 - Applies to cases with high levels of residual disease: more than 5 x 10⁹/l circulating CLL cells or 30% CLL cells in the BM,
- B-cell CLL – MRD-positive at iwCLL threshold (≥0.01%)
 - Applies to cases with residual disease detectable at or above the iwCLL 0.01% threshold and so not to be considered for treatment cessation.
- B-cell CLL – MRD-negative at iwCLL threshold (<0.01%)
 - Applies to cases eligible for stopping rules, either with no detectable residual disease or with very low levels of detectable disease below 0.01%.
- Other diagnoses, e.g. “see comments” or “inadequate sample”
 - Applies to cases in which the MRD status cannot be determined at the 0.01% threshold. Interpretation of cases with such a diagnosis should be reviewed by the CI and the Clinical Coordinators.

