12.2 Analysis of Outcome Measures

12.2.1 IcICLE (initial phase)

Statistical analysis in this study, will be based on descriptive statistics only.

The primary endpoint is the dichotomous variable, MRD Negativity. The precise specification for determining whether a patient is MRD-negative is detailed in section 7.2.3

The number and proportion of patients in each response category will be reported with 95% confidence interval and presented as a proportion of the total number of patients recruited to this study.

- The number and proportion of patients experiencing any grade haematological and non-haematological toxicities will be reported as a proportion of the number of patients recruited.
- Survival estimates will be calculated using the method of Kaplan and Meier, and point estimates reported with 95% CIs.
- The number and proportion of patients with abnormalities in chromosome 11 or 17, or with an unmutated IGHV gene will be reported.

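### Protocol section 12.2.2 gives n in the extension's activity rule as patients who finished treatment but elsewhere as all patients; the literal reading can turn a rejection into an approval.

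*Protocol*

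**What the plan says.** Protocol section 12.2.2 sets out the whole decision rule. The prior is uniform ("This is achieved using a Beta(1, 1) distribution"). The regimen is approved "if we are at least 50% confident that the level of activity exceeds 20" per cent. The posterior is Beta(1+r, 1+n-r), and the one sentence that says who is in n reads "After n patients have completed treatment, r of whom become MRD-negative, our posterior beliefs about the activity rate will be described by".

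Other text on the same rule points elsewhere:

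- Section 12.2.2 applies the rule when target recruitment is reached and "sufficient follow-up has been completed to inform activity status for all patients".
- Table 8 in that section heads the n column as total patients.
- The performance claims are indexed by trial size: "For all trial sizes between 30 and 40 patients inclusive, the activity decision rule has the following operating characteristics". They are approval above 90% at a true rate of 30%, approval below 10% at a true rate of 10%, and no approval below an 18.7% response share. The section ties sizes under 40 to shortfalls in recruitment.
- For the initial phase, section 12.2.1 is explicit: response categories are "presented as a proportion of the total number of patients recruited to this study". The extension has no matching sentence.

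Section 7.2.3.2 also has a laboratory report category that "Applies to cases in which the MRD status cannot be determined at the 0.01% threshold", and refers such cases for review.

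**The concern.** A denominator of patients who finished treatment drops those who stopped early for toxicity or other reasons. If most of them are not MRD-negative, the response share rises although no more patients have responded, and the result no longer describes the patients who entered the study.

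The phrase also has no stable meaning here. Ibrutinib runs until progression or confirmed MRD negativity (sections 7.1 and 7.2.3), obinutuzumab is given for up to 6 cycles, and a patient who stops one drug may continue the other (section 7.11.2). On one reading finishing depends on the outcome; on another, anyone who stops obinutuzumab early leaves n.

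The rule decides whether the combination goes forward to a larger randomised trial. With at most 40 patients and no control arm, a few patients in or out of n can settle that decision, and two readings of n leave room to choose between them after the data are seen.

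**Working it through.** **Inputs.** Beta(1,1) prior, 20% activity threshold, 50% posterior cut-off, sizes 30 to 40, and the claims of <10%, >90% and 18.7%: all from section 12.2.2. Maximum size 40: section 12.5.2. The number of patients excluded, d, is not in the protocol; it is an assumption, shown over a range.

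**Step 1. Reproduce the plan.** The posterior probability is Pr(θ > 0.2) under Beta(1+r, 1+n−r).

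| r / n | Posterior | Pr(θ > 0.2) | Decision |
|---|---|---|---|
| 8 / 40 | Beta(9, 33) | 56.19% | approve |
| 7 / 40 | Beta(8, 34) | 40.69% | reject |
| 7 / 37 | Beta(8, 31) | 50.03% | approve |
| 6 / 35 | Beta(7, 30) | 40.07% | reject |

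All four rows of Table 8 agree. For each n, take the smallest approving r and the exact binomial upper tail. For n = 30 to 40, approval at a true 10% is 3.2% to 9.4% (maximum at n = 32) and approval at a true 30% is 90.6% to 95.6%. The lowest approving share is 6/32 = 18.75%. The stated operating characteristics are correct when n is the trial size.

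**Step 2. Reversal.** Register 40 patients, 7 of them MRD-negative: reject at 40.69%. Drop three non-responders who stopped early: n = 40 − 3 = 37, r = 7, approve at 50.03%. Yet 7/40 = 17.5%, below the 18.7% floor the section promises.

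**Step 3. False approval.** Register N patients with a true rate of 10% among all registered. Exclude d, all taken as not MRD-negative. Then n = N − d, the rate among those left is 0.10 × N/(N − d), and false approval is the binomial tail at the cut-off for N − d. Example: N = 40, d = 8 gives n = 32, cut-off 6, rate 4/32 = 0.125, and Pr(X ≥ 6) = 20.4%.

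| N | d | n | Cut-off | False approval |
|---|---|---|---|---|
| 40 | 0 | 40 | 8 | 4.2% |
| 40 | 1 to 2 | 39 to 38 | 8 | 4.1-4.2% |
| 40 | 3 to 7 | 37 to 33 | 7 | 9.7-9.9% |
| 40 | 8 | 32 | 6 | 20.4% |
| 36 | 0 | 36 | 7 | 6.3% |
| 36 | 4 | 32 | 6 | 14.4% |
| 36 | 6 | 30 | 6 | 14.3% |
| 35 | 3 | 32 | 6 | 13.1% |
| 33 | 1 | 32 | 6 | 10.6% |
| 30 | 3 | 27 | 5 | 17.4% |

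The smallest d that passes 10%, for N = 30 to 40 in order, is 3, 4, 5, 1, 2, 3, 4, 5, 6, 7, 8.

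**Scale of d.** The toxicity guideline in section 12.6.2 tolerates up to 6 of 36 patients ceasing therapy for toxicity. At N = 36, dropping 6 non-responders turns 6/36 (36.98%, reject) into 6/30 (57.11%, approve).

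**The case against.** The strongest reply is that the sentence only explains conjugate updating, and that everything operative points to all patients: the trigger for the rule, the heading in Table 8, the indexing by trial size, and the link between small n and recruitment. Nothing in the section says that early discontinuers are removed. The literal reading also defeats itself. A patient who becomes MRD-negative during obinutuzumab receives 12 more months of ibrutinib after it (section 7.2.3.1), while the primary analysis follows the 9 month assessment (section 12.4). No responder could by then have finished ibrutinib under the stopping rules.

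Much of this stands. A reader might infer that the protocol settles on a completers-only count; it does not. What remains is that the sentence introducing n conflicts with the text around it, and that reading it as completing the obinutuzumab cycles is still workable.

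A reader might also infer that false approval must exceed 10%. It need not: at N = 40 it stays below 10% until the eighth exclusion. Eight of 40 could be drawn from section 1.4.1, where "the incidence of AEs leading to withdrawal of any study medication was 20.2% and 15.3%, respectively" for the two chlorambucil combinations, the first being the obinutuzumab arm. That is a different regimen, and withdrawal of one drug is not departure from this study, so the figure is no forecast. Some discontinuers may already be MRD-negative, because the endpoint counts results at or before 9 months; that would reduce the effect. And if 10% is taken as the rate among finishers and 30 to 40 finish, the bound holds (maximum 9.4%), though it then no longer describes registered patients.

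Detailed analysis populations may properly sit in a statistical analysis plan. This point concerns conflicting statements about a rule that the protocol itself fixes.

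**Conclusion.** The concern holds as an internal conflict over the denominator of the primary decision rule. Applied as written, the sentence can change the decision: three non-responders removed from 40 are enough when 7 have responded. The effect on false approval is conditional. At N = 40 it roughly doubles with 3 to 7 exclusions but stays under the stated 10%, and reaches 20.4% with 8. At N = 33 to 36 one to four exclusions pass 10%, and at N = 30 three do. These figures assume that every excluded patient is a non-responder and that the true rate among all registered patients is 10%; the number excluded is not known from the protocol. The stated operating characteristics themselves are correct and need no change once n is every registered patient.

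**What to change.** In section 12.2.2, replace the reference to patients finishing treatment with a definition such as: n is the number of patients registered to the extension study; r is the number of these who meet the peripheral blood and bone marrow MRD-negative endpoint at or before the 9 month assessment; a patient without such a result, for whatever reason, is counted as not MRD-negative. This agrees with the rest of the section, with Table 8 and with the recruited denominator of section 12.2.1. It also covers early discontinuers and samples whose MRD status remains undetermined after review. A posterior restricted to patients who finished obinutuzumab may be shown as a sensitivity analysis, without a role in the decision.

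With this definition, false approval is 3.2% to 9.4% and approval at a true 30% is 90.6% to 95.6% for N = 30 to 40, so Table 8 and the stated claims stand. The cost is one sentence and no extra patients; the observed rate may be slightly lower than under a completers count.

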12.3 Planned Sub Group Analyses

The data from the initial and Extension phases of the study will be analysed separately.

In the initial phase, the two-cohorts, A and B(i), will be analysed separately. The immunoglobulin mutation status (mutated [$>98\%$ similarity to germ-line] versus unmutated [$>98\%$ similarity to germ-line]) will be analysed separately as will patients with 17p deleted and 11q deleted CLL.

In the extension phase the same analysis applies to the two cohorts B(ii) and B(iii)..

12.4 Timelines for Analysis

The data from the initial and Extension phases of the study will be analysed separately.

In the initial phase the first primary analysis of primary and secondary outcome measures will occur within 3 months of the final patient being assessed for primary outcome. (which is assessed at 6 months of trial treatment) Subsequent final analyses of all outcome measures is planned 2 years after the final patient is registered into the initial phase.

For the extension phase, the first primary analysis of primary and secondary outcome measures will occur within 3 months of the final patient being assessed for primary outcome (which is assessed at 9 months of trial treatment). Subsequent final analyses of all outcome measures is planned 2 years after the final patient is registered to the Extension phase.

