7.10 Patient Follow Up

All patients will remain on study treatment for at least 12 months unless their disease progresses or the patient achieves clinical complete remission or MRD-negative remission according to the modified IWCLL Response Criteria. Guidance for patients achieving an MRD-negative remission is given in Section 7.2.3.

After they have received ibrutinib treatment for a minimum of 6 months, patients in the relapsed/refractory IcICLLe cohort (B(i)) may be given the option to continue treatment via the IcICLLe extension study.

Patients in the treatment naïve cohort of IcICLLe who have stable disease or have maintained a response will remain on ibrutinib treatment, with the cost of ibrutinib paid for by collaborating pharmaceutical company, until disease progression or confirmed MRD negative remission.

All patients will be followed up for trial outcome measures until death.

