11. END OF TRIAL DEFINITION

The trial end date is deemed to be 6 months after the last patient has completed the protocol defined interventional treatment. This will allow sufficient time for the completion of protocol procedures, data collection and data input.

The Trials Office will notify the MHRA and REC that the trial has ended at the appropriate time and will provide them with a summary of the clinical trial report within 12 months of the end of trial.

Sites should continue to notify the Trials Office of changes in Principal Investigator by completing and returning (where required) an Investigator Registration Form together with a current signed and dated CV until otherwise notified.

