12.1.2 Secondary Objectives / Outcome Measures

- Best disease response, whether complete remission (CR), complete remission with incomplete marrow recovery (Cri) or partial remission (PR), to treatment in a) the initial phase of the study at or before the 6 month assessment and b) the Extension Study at or before the 9 month assessment. Independent decisions will be made for each study (initial and extension)., assessed according to the IWCLL Criteria (revised 2008) (Appendix 1). The dynamics of response will be assessed both in terms of the change in absolute levels of CLL in the blood and marrow as well as the changes in the proliferating compartment and changes in chemokine receptor.
- 1 and 2 year progression free survival for relapsed/refractory and treatment naïve patients defined as time from date of registration to date of progression (per the modified 2008 IWCLL criteria) or death from any cause. Alive patients who are progression free will be censored at their date of last follow-up.
- 1 and 5 year overall survival for relapsed/refractory and treatment naïve patients is defined as the time from date of registration to the date of death from any cause.
- Toxicity of ibrutinib and obinutuzumab
- CLL cell levels as a percentage of total leucocytes in the bone marrow (BM) and absolute counts in the peripheral blood (PB).
- The proportion of patients with >5%, 0.5-5%, <0.5% CLL cells in cell cycle (expressing Ki67) in the peripheral blood and bone marrow in a) the initial phase of the study at or before the 6 month assessment and b) the Extension Study at or before the 9 month assessment
- Change in the expression levels of CD10, CD103, CD11c, CD185, CD196, CD20, CD200, CD22, CD23, CD25, CD27, CD305, CD31, CD38, CD39, CD43, CD49d, CD5, CD79b, CD81, CD95, IgD, IgG, or IgM on CLL cells relative to baseline by more than 50% and at least 500 arbitrary units in median fluorescence intensity.

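### Section 12.4 sets the final analysis of all outcomes 2 years after last registration, which is inconsistent with the secondary outcome of 5-year overall survival

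*Protocol*

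**What the plan says.** Section 12.4 plans two analyses per phase. The first follows within 3 months of the last patient's primary-outcome assessment, at 6 months of treatment in the initial phase and 9 months in the extension. The second is the final one. For the initial phase: "Subsequent final analyses of all outcome measures is planned 2 years after the final patient is registered into the initial phase". For the extension: "Subsequent final analyses of all outcome measures is planned 2 years after the final patient is registered to the Extension phase".

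The time-to-event outcomes are in section 12.1.2, and the synopsis and section 2.2 give the same landmarks. One is "1 and 2 year progression free survival for relapsed/refractory and treatment naïve patients". The other is OS: "1 and 5 year overall survival for relapsed/refractory and treatment naïve patients is defined as the time from date of registration" to death from any cause.

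Three other places bear on the point:
- Section 12.2.1 gives the estimator for the initial phase: "Survival estimates will be calculated using the method of Kaplan and Meier, and point estimates reported with 95% CIs".
- Section 7.10 sets the length of follow-up: "All patients will be followed up for trial outcome measures until death".
- Section 11 defines the close of the trial: "The trial end date is deemed to be 6 months after the last patient has completed the protocol defined interventional treatment".

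**The concern.** The date in section 12.4 is described as final and as covering every outcome measure. Two years after the last registration suits 1- and 2-year progression-free survival (PFS) and 1-year OS, but it falls 3 years before the last patient can reach the 5-year OS landmark. A pre-specified secondary outcome is thus tied to an analysis that comes too early for it.

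Two things are at stake. If the schedule is followed, the final report contains either no 5-year OS estimate or an imprecise one from the earliest registrants. If 5-year OS is reported later, it comes from an analysis the protocol did not plan, at a data cut chosen after the earlier results were known.

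**Working it through.** The plan gives no calculation for this point, so there is no figure to reproduce. The check is arithmetic on dates.

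**Inputs**
- Lag from last registration to final analysis: L = 2 years in each phase (section 12.4).
- Landmark: 5 years from registration (section 12.1.2).
- Cohort size: 20 per cohort in the initial phase (section 12.5.1). In the extension, up to 20 in cohort (B)iii, at least 20 in (B)ii and no more than 40 in all (section 12.5.2). Section 12.3 analyses the cohorts separately, so 20 is the working denominator.
- Accrual period A: not stated. It is an assumption, shown from 0.5 to 5 years, with registrations spread evenly over the period within each cohort.

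**Last registrant**

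Follow-up at the final analysis is 2 × 12 = 24 months, against 5 × 12 = 60 months needed. The shortfall is 60 − 24 = 36 months. Only a patient registered at least 36 months before the last one can have reached 5 years.

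**Whole cohort**

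Potential follow-up runs from L (last patient) to A + L (first patient). The share with more than 5 years is

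share = max(0, min(1, (A + L − 5) / A)).

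With L = 2:
- A = 0.5, 1, 2 and 2.5 years: the longest follow-up is 2.5, 3, 4 and 4.5 years. Nobody reaches 5 years.
- A = 3 years: the longest is exactly 5.0 years; share = (3 + 2 − 5)/3 = 0%.
- A = 3.5 years: share = 0.5/3.5 = 14%, or 2.9 of 20.
- A = 4 years: share = 1/4 = 25%, or 5 of 20.
- A = 5 years: share = 2/5 = 40%, or 8 of 20.

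These counts are ceilings, because they count potential follow-up; deaths and losses reduce the number still at risk at 5 years.

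**What this does to the estimate**

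When the longest follow-up is below 5 years and ends in a censored patient, the Kaplan-Meier curve stops before the landmark and has no value there. When a minority has passed 5 years, a value exists, but the last part of the curve depends on few patients, all of them early registrants.

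**Other landmarks at the same date**

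Every patient has at least 2 years of potential follow-up, so 1- and 2-year PFS and 1-year OS are fully served. Only 5-year OS is out of line.

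**After the fix**

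With L = 5 for OS, share = (A + 5 − 5)/A = 1 for any A. All 20 of 20 patients in a cohort have at least 5 years of potential follow-up.

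**The case against.** The strongest defence is that nothing is lost. Section 7.10 keeps all patients under follow-up for outcome measures until death. Section 12.4 says only what is planned and does not forbid a later survival update. This stands, and it limits the point to analysis timing. It does not remove the inconsistency, since section 12.4 calls the 2-year analysis final, extends it to all outcome measures and names no successor.

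A second defence is that the analysis plan could settle the matter. Had section 12.4 been silent, that would be a fair answer. It is not silent, and a later document that added a 5-year analysis would have to depart from it.

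Third, the extension phase is less clear-cut than the initial phase. Section 12.1.2 splits best response and Ki67 by phase but does not split OS, and section 12.2.2 does not mention survival analysis. Cohort (B)iii patients register a second time (section 6), and the OS definition does not say which registration starts the clock. If it is the first, they have at least 6 months more follow-up than the calculation gives them. These are reasons to confine the remedy to each phase for which 5-year OS is reported.

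Fourth, the outcome carries little weight in the design. The initial phase is descriptive, and the extension's activity decision rule rests on MRD negativity alone. That is correct and bears on how serious the point is.

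A reader might also infer that 5-year OS cannot be estimated at all, or that no patient in any cohort will have 5 years of follow-up. The protocol does not support this as a general statement: it holds only if accrual takes 3 years or less, and no accrual period is given.

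**Conclusion.** The final-analysis date in section 12.4 is wrong as written for one secondary outcome and should be corrected. The 36-month shortfall for the last registrant follows from the document alone. How many patients reach 5 years depends on the assumed accrual length: none at 3 years or less, and about 14%, 25% and 40% at 3.5, 4 and 5 years under uniform accrual. Uneven accrual would shift these shares. So would a cohort that filled well before its phase closed, because section 12.4 counts from the last patient in the phase rather than in the cohort.

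The finding does not extend to data collection, the primary MRD endpoint, the activity decision rule, the toxicity stopping guidelines, 2-year PFS or 1-year OS. It is a should-fix inconsistency between an outcome definition and an analysis date. It is not a design that prevents 5-year survival from being obtained.

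**What to change.** In section 12.4, for each phase:
- Keep the analysis 2 years after the last registration as the final analysis of all outcome measures except 5-year OS. The exception should be no wider than that. Restricting the 2-year analysis to PFS and 1-year OS would leave toxicity, CLL cell levels, marker expression and the exploratory outcomes without a stated final analysis.
- Add an OS analysis 5 years after the last registration in each phase for which 5-year OS is reported, using the follow-up that section 7.10 already requires.

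Then check section 11. The end of trial depends on when the last patient completes treatment, a date that cannot be known in advance and is not tied to the 5-year data cut. If ending the trial would stop survival data collection, section 11 needs a provision that keeps it open until that cut. This could mean amending the end-of-trial definition itself.

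The cost is a revision of section 12.4, one later Kaplan-Meier analysis per phase concerned, later reporting of 5-year OS and, if the check shows the need, a change to section 11. No extra patients or visits are required.
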